7.1. Time and Events Table

Table 1 Screening assessments for subjects administered AVA or co-administered raxibacumab and AVA

Screening Assessments	Days -36 to -15 ^a	Notes
Informed consent process	X	
Demographic information	X	
Inclusion/Exclusion criteria	X	
Medical history (includes substance usage and Family history of premature CV disease)	X	
Physical exam including height and weight	X	
Alcohol and Drug Screening	X	
Urinalysis	X	
Vital signs	X	
Hematology and clinical chemistry	X	Refer to Table 4 for specific laboratory tests.
HIV, Hep B and Hep C screen	X	
Review concomitant medications	X	
Serum or urine pregnancy test	X	
AE/SAE assessment	X	Will capture SAEs reported between Screening visit and Day -1.
Toxin Neutralizing Ab (TNA)	X	
Anti-PA Ab	X	

a. The screening window closes at Day -15 to allow all analyses to be completed to confirm subject eligibility.

Table 2 Treatment Group 1: Time and Events for subjects administered AVA

Protocol Activity	Study Visit						Notes
Assessments	Day -1 ^a	Day 1	Day 15 (± 2 days)	Day 29 (± 2 days)	Day 57 (± 2 days)	Day 183 (± 4 days)	
Inpatient visit	←X→						
Outpatient visit				←-----X-----→			
Urinalysis					X		
Admit to unit	X						
Randomization	X						
Discharge from unit		X					The subject will be discharged from the unit after all assessments are completed.
Vital signs	X	X		X	X	X	
Hematology and clinical chemistry	X			X	X		Refer to Table 4 for specific laboratory tests. On Day 29 the specimen will be collected prior to AVA injection.
Review concomitant medications	X		X	X	X	X	
Serum or urine pregnancy test	X		X	X	X	X	
AVA administration		X	X	X			Each sequential AVA injection will be administered in a different injection site (e.g. alternating arms).
AE/SAE assessment	X	X	X	X	X	X	
Toxin Neutralizing Ab (TNA)		X		X	X	X	On Days 1 and 29 the specimen will be collected prior to AVA injection.
Anti-PA Ab		X		X	X	X	On Days 1 and 29 the specimen will be collected prior to AVA injection.

a. Day -1 is the calendar day preceding Day 1; the designation "Day 0" is not used in this study.

Table 3 Treatment Group 2: Time and Events Table for subjects co-administered raxibacumab and AVA

Protocol Activity Assessments	Study Visit								Notes	
	Day -1 ^a	Day 1				Day 15 (± 2 days)	Day 29 (± 2 days)	Day 57 (± 2 days)	Day 183 (± 4 days)	
		pre-raxi infusion	0 hr	0.5 hr (± 5 min)	2-6 hrs					
Inpatient visit		X								
Outpatient visit						X				
Urinalysis										
Admit to unit	X									
Randomization	X									

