Discharged from unit			X							The subject will be discharged from the unit after all assessments are completed.
Vital signs	X		X			X	X	X		
Hematology and clinical chemistry	X					X	X			Refer to Table 4 for specific laboratory test. On Day 29 the specimen will be collected prior to treatment administration.
Review concomitant medications	X				X	X	X	X		
Serum or urine pregnancy test	X				X	X	X	X		
Diphenhydramine administration		X								Diphenhydramine (25-50 mg) must be administered within 60 minutes prior to the raxibacumab infusion.
Raxibacumab administration			X							Raxibacumab infusion must be completely administered prior to first AVA dose on Day 1 and administered in opposite limb from AVA injection.
AVA administration			X			X	X			Each sequential AVA injection will be administered in a different injection site (eg. alternating arms).
AE/SAE assessment	X	X	X	X	X	X	X	X		
PK sampling		X	X	X	X	X	X	X	X	A blood specimen will be collected prior to raxibacumab infusion, 30 minutes post raxibacumab infusion (± 5 min), 2-6 hours post infusion on Day 1, and at Days 15, 29, and 57 (14, 28, and 56 days post raxibacumab administration). An additional sample will be collected at the Day 183 visit.
Anti-raxibacumab Ab		X					X	X		
Toxin Neutralizing Ab (TNA)		X					X	X	X	The Day 29 specimens will be collected prior to AVA administration.
Anti-PA Ab		X					X	X	X	The Day 29 specimens will be collected prior to AVA administration.

a. Day -1 is the calendar day preceding Day 1; the designation "Day 0" is not used in this study.

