7.4.1.1. Time Period and Frequency for Collecting AE and SAE Information

AEs and SAEs will be collected from the start of study treatment until the follow-up contact (see Section [7.4.1.3](#)), at the timepoints specified in the Time and Events Table (Section [7.1](#)).

Medical occurrences that begin prior to the start of study treatment but after obtaining informed consent may be recorded on the Medical History/Current Medical Conditions section of the CRF.

Any SAEs assessed as related to study participation (e.g., protocol-mandated procedures, invasive tests, or change in existing therapy) or related to a GSK product will be recorded from the time a subject consents to participate in the study up to and including any follow-up contact.

All SAEs will be recorded and reported to GSK within 24 hours, as indicated in [Appendix 4](#).

Investigators are not obligated to actively seek AEs or SAEs in former study subjects. However, if the investigator learns of any SAE, including a death, at any time after a subject has been discharged from the study, and he/she considers the event reasonably related to the study treatment or study participation, the investigator must promptly notify GSK.

NOTE: The method of recording, evaluating and assessing causality of AEs and SAEs plus procedures for completing and transmitting SAE reports to GSK are provided in [Appendix 4](#).

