7.4.1.2. Method of Detecting AEs and SAEs

Care will be taken not to introduce bias when detecting AEs and/or SAEs. Open-ended and non-leading verbal questioning of the subject is the preferred method to inquire about AE occurrence. Appropriate questions include:

- “How are you feeling?”
- “Have you had any (other) medical problems since your last visit/contact?”
- “Have you taken any new medicines, other than those provided in this study, since your last visit/contact?”

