9.4.2.3. Safety Analyses

Clinical safety observations will include AEs, urinalysis, vital sign measurements, and clinical laboratory assessments. Safety data will be tabulated and, where appropriate, analyzed by the use of descriptive statistics. Safety data will be tabulated for the Safety Population.

The number (%) of subjects withdrawing from the study will be summarized for each treatment group and the number (%) subjects withdrawing for each individual reason will be summarized by treatment group.

Reported AEs will be coded using MedDRA. The number (%) of subjects in each treatment group with treatment-emergent AEs will be compared for overall incidence and by system organ class and preferred term. Similar summaries will also be presented for deaths, all SAEs, AEs leading to withdrawal, and drug-related AEs. Severity of treatment-emergent AEs will also be summarized by system organ class, preferred term, and treatment group.

Additionally, the frequency of laboratory abnormality events along with shifts from baseline will be summarized, as well as changes over time in laboratory parameters, urinalysis and vital signs.

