4.12.4 Safety Analyses

All safety assessments, including AEs, clinical laboratory evaluations, and vital signs will be listed and where appropriate summarized with descriptive statistics.

4.12.4.1 *Summary of Exposure*

Study treatment administration will be listed and summarized for AVA with the number (%) of subjects receiving dose on Day 1, Day 15 and Day 29.

4.12.4.2 *Adverse Events*

An AE is any untoward medical occurrence in a patient or clinical investigation subject, temporally associated with the use of a medicinal product, whether or not considered related to the medicinal product. An AE can therefore be any unfavorable and unintended sign (including an abnormal laboratory finding), symptom, or disease (new or exacerbated) temporally associated with the use of a medicinal product. The period of observation for AE reporting will begin from the start of study treatment until the follow-up contact.

All AEs will be coded to body system and preferred term using the Medical Dictionary for Regulatory Activities (MedDRA) dictionary, 17.1.

A treatment-emergent adverse event (TEAE) is defined as any AE that began or worsened following the start of dosing. A treatment-related AE is defined as any TEAE that is assessed by the Investigator as having a reasonable possibility that the AE may have been caused by the study treatment or those for which the relationship is missing.

The total number and percentage of subjects with TEAEs will be presented by system organ class and preferred term for each study treatment and for all subjects overall. Treatment-emergent adverse events will also be presented by maximum grade according to the Division of Microbiology and Infectious Diseases (DMID) toxicity tables (Appendix 6 of the study protocol). For AEs not included in the appendix above, the following guidelines will be used:

Mild: An event causing no limitation of usual activities.

Moderate: An event causing some limitation of usual activities.

Severe: An event causing inability to carry out usual activities.

Life threatening: An event that is potentially life threatening or disabling.

Treatment-emergent adverse events will be tabulated presenting the system organ class alphabetically and within each system the preferred term will be presented in decreasing order of the total number of subjects who experienced each TEAE. Treatment-related adverse events will be similarly presented.

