APPENDIX A. PARTIAL DATE CONVENTIONS

Imputed dates will NOT be presented in the listings.

ALGORITHM FOR TREATMENT EMERGENCE OF ADVERSE EVENTS:

START DATE	STOP DATE	ACTION
Known	Known	If start date < study med start date, then not TEAE If start date >= study med start date, then TEAE
	Partial	If start date < study med start date, then not TEAE If start date >= study med start date, then TEAE
	Missing	If start date < study med start date, then not TEAE If start date >= study med start date, then TEAE
Partial, but known components show that it cannot be on or after study med start date	Known	Not TEAE
	Partial	Not TEAE
	Missing	Not TEAE
Partial, could be on or after study med start date	Known	If stop date < study med start date, then not TEAE If stop date >= study med start date, then TEAE
	Partial	Impute stop date as latest possible date (i.e. last day of month if day unknown or 31st December if day and month are unknown), then: If stop date < study med start date, then not TEAE If stop date >= study med start date, then TEAE
	Missing	Assumed TEAE
Missing	Known	If stop date < study med start date, then not TEAE If stop date >= study med start date, then TEAE

START DATE	STOP DATE	ACTION
	Partial	
Impute stop date as latest possible date (i.e. last day of month if day unknown or 31st December if day and month are unknown), then:
 
If stop date < study med start date, then not TEAE
 
If stop date >= study med start date, then TEAE

	Missing	Assumed TEAE

ALGORITHM FOR PRIOR / CONCOMITANT MEDICATIONS:

START DATE	STOP DATE	ACTION
Known	Known	
If stop date < study med start date, assign as prior
 
If stop date >= study med start date and start date <= end of treatment, assign as concomitant
 
If stop date >= study med start date and start date > end of treatment, assign as post study

	Partial	
Impute stop date as latest possible date (i.e. last day of month if day unknown or 31st December if day and month are unknown), then:
 
If stop date < study med start date, assign as prior
 
If stop date >= study med start date and start date <= end of treatment, assign as concomitant
 
If stop date >= study med start date and start date > end of treatment, assign as post treatment

	Missing	
If stop date is missing could never be assumed a prior medication
 
If start date <= end of treatment, assign as concomitant
 
If start date > end of treatment, assign as post treatment

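### Day 1 AE enquiry is scheduled at least three times with raxibacumab and once with AVA alone, and the whole-study TEAE comparison neither separates Day 1 nor notes the difference

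*Protocol*

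**What the plan says.** Protocol Section 9.4.2.3 states that "The number (%) of subjects in each treatment group with treatment-emergent AEs will be compared for overall incidence", and by system organ class and preferred term. SAP Section 4.12.4.2 states: "The total number and percentage of subjects with TEAEs will be presented by system organ class and preferred term for each study treatment". Neither document divides TEAEs by time of onset or mentions that the arms are questioned on different schedules. Both treat safety descriptively, with no confidence interval, test or decision rule for AEs.

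Protocol Section 7.4.1.1 collects AEs "at the timepoints specified in the Time and Events Table". In Section 7.1, the row for the AVA-alone group (Table 2) reads "AE/SAE assessment X X X X X X", and the row for the raxibacumab + AVA group (Table 3) reads "AE/SAE assessment X X X X X X X X". SAP Tables 2.2 and 2.3 have the same counts. Table 3 divides Day 1 into four columns: before the infusion, 0 hr, 0.5 hr and 2-6 hr. Table 2 has one undivided Day 1 column.

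Protocol Section 7.4.1.2 promises "Care will be taken not to introduce bias when detecting AEs and/or SAEs" and relies on open-ended verbal questions, one of which asks about problems since the previous contact. Section 6.3 confirms that the study is open-label.

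SAP Section 4.12.4.2 counts an AE as treatment-emergent if it starts or worsens once dosing has begun, and sends earlier AEs to listings only. Appendix A applies the rule by date: "If start date >= study med start date, then TEAE".

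**The concern.** Describing the safety of the combination against AVA alone is a stated secondary objective, and the side-by-side TEAE percentages are the main evidence for it. AE summaries also go to the unblinded reviewers at both interim analyses (SAP Section 4.9). If one arm is asked about AEs more often on the day both products are given, a transient complaint has more chances to be recorded there.

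Day 1 is also when genuine infusion reactions would appear. Protocol Section 4.6 names them as the study-drug risk, and only the raxibacumab group receives an infusion and premedication. A real effect and an ascertainment effect would therefore sit in the same table cell with nothing to distinguish them.

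A smaller issue concerns Day 1 onsets. A complaint that begins on Day 1 before any dose is not treatment-emergent under the SAP definition, but it is under the Appendix A date comparison. Only the raxibacumab group has a separate pre-infusion column on that day in which such a complaint could be elicited.

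**Working it through.** The plan states no figure for this point, so there is none to reproduce. The check is a count of scheduled assessments followed by an illustrative capture model.

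**Count.** AVA alone (Protocol Table 2, SAP Table 2.2): 6 marks over 6 columns (Days -1, 1, 15, 29, 57, 183), so 1 on Day 1. Raxibacumab + AVA (Protocol Table 3, SAP Table 2.3): 8 marks over 9 columns, of which 5 lie outside Day 1. At least 8 - 5 = 3 marks fall on Day 1, and at most 4. The columns of Table 3 are displaced in the text as read from the PDF, so which columns are marked cannot be settled; that is not a fault in the plan.

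**Enquiries after the infusion starts.** If all four Day 1 columns are marked, 3 follow the start. If three are marked, it is 3 when the unmarked column is the pre-infusion one and 2 otherwise. The contrast is therefore k = 2 or 3 against 1, taking the AVA-alone enquiry to follow the AVA dose. Table 2 does not say so; if it came before the dose, the gap would be wider.

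**Model.** All inputs are assumptions:
- p: share of subjects with a Day 1 event, equal in both arms
- q: chance that one Day 1 enquiry captures it
- r: chance that Day 15 questioning recovers an event missed on Day 1

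Captured share with one enquiry: 1 - (1-q)(1-r). With k enquiries: 1 - (1-q)^k (1-r).

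Tilt = p(1-r)[(1-q) - (1-q)^k].

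Example: p = 10%, q = 0.8, r = 0.5, k = 2 gives 0.10 × 0.5 × (0.2 - 0.04) = 0.008, or 0.8 points.

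| p | q | r | Tilt, k=2 (points) | Tilt, k=3 (points) |
|---|---|---|---|---|
| any | 1.0 | any | 0 | 0 |
| any | any | 1.0 | 0 | 0 |
| 5% | 0.8 | 0.5 | 0.40 | 0.48 |
| 10% | 0.8 | 0.5 | 0.80 | 0.96 |
| 10% | 0.5 | 0.5 | 1.25 | 1.88 |
| 10% | 0.5 | 0 | 2.50 | 3.75 |
| 20% | 0.8 | 0 | 3.20 | 3.84 |
| 20% | 0.5 | 0 | 5.00 | 7.50 |

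Over the grid tried (p = 5, 10, 20%; q = 0.5, 0.8, 1; r = 0, 0.5, 0.8, 1), every case except the last row is below 4 points. With 267 subjects per arm, 0.8 points is about 2 subjects (0.008 × 267 = 2.1), 3.75 points about 10 (0.0375 × 267 = 10.0) and 7.5 points about 20 (0.075 × 267 = 20.0).

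**Any TEAE.** A subject with another TEAE counts already. If half of subjects have one, the tilt halves: 3.75 becomes 1.88 and 7.5 becomes 3.75.

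**The case against.** The strongest reply is that the measure is subjects with an event, not reports. SAP Section 4.12.4.2 counts a subject once per preferred term, collection starts with study treatment in both arms, and each enquiry reaches back to the last contact. Day 15 therefore covers the rest of Day 1. A tilt arises only for a transient event that the single Day 1 enquiry misses and the subject does not report at Day 15. This stands, and it limits the size. It removes the problem only if one of those two captures is complete.

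A reader might infer that the comparison is tilted by construction, for example by letting each enquiry generate AEs independently: at 3% each, 1 - 0.97^3 = 8.7% against 3.0% on Day 1. The documents do not support this. It ignores the look-back wording and Day 15 recall, counts a possible pre-infusion enquiry as post-dose, and describes Day 1 alone, not the pooled table. Nor is an error rate inflated, because no test or interval for AEs is planned.

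The mark counts deserve some caution. In the extracted Table 3 the PK row shows 8 marks while its own note lists 7 specimens. The AE row, however, reads 8 in both documents. One mark in an undivided Day 1 column also does not prove that only one question is asked that day.

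On pre-dose complaints, Protocol Section 7.4.1.1 allows them to be entered as medical history, the date rule applies to both arms, and diphenhydramine is itself listed as study treatment (Section 6.1), so some pre-infusion complaints may properly follow the start of treatment. This narrows the definitional point but leaves the two SAP rules inconsistent for Day 1.

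**Conclusion.** The point holds in limited form. Scheduled Day 1 enquiry is unequal, at least three against one and two or three against one after the infusion starts, and the whole-study TEAE comparison neither separates nor acknowledges it. Under the capture model the tilt is zero or against raxibacumab: 0 to about 4 percentage points in most cases tried, 7.5 at the extreme, less for any TEAE. The size rests wholly on assumed event and capture rates, and the schedule does not fix it.

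No formal inference is invalidated. What suffers is interpretation: a Day 1 excess could be genuine, an artefact of questioning, or both. A reader might conclude that the arms should be compared only on events after Day 1. That does not follow, because it would drop infusion reactions, the study-drug risk the protocol itself names.

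**What to change.** 1. In SAP Section 4.12.4.2, keep the overall TEAE table, Day 1 included, as the headline. Add a by-arm split by onset (Day 1 versus after Day 1), with a footnote that Day 1 enquiry was unequal and that a Day 1 excess may be genuine. Do not rest the between-arm statement on after-Day-1 data alone. Cost: one further cut of existing data and a longer set of tables.
2. If enrolment allows, ask the AVA-alone group the same Day 1 AE questions at matching times while they are in the unit. Cost: a few verbal questions per subject and possibly a few more hours' stay. This is the only change that reduces the imbalance; the first only exposes it.
3. Reconcile the TEAE definition in SAP Section 4.12.4.2 with the date-only rule in Appendix A for Day 1 onsets, using AE onset time if it is collected. Protocol Section 6.6 records the time of each dose, but the documents do not say that AE onset time is recorded. If it is not, state the date-only rule as a limitation.

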9.4.2.4. Statistical Analysis of Pharmacokinetic Data

Drug concentration-time data will be listed for each subject and summarized by descriptive statistics at each nominal collection time. PK parameters will be listed for each subject and summarized by descriptive statistics.

Specimens will also be analyzed for the presence of anti-raxibacumab antibodies. Those results will be descriptively and/or graphically summarized as appropriate to the data.

10. STUDY GOVERNANCE CONSIDERATIONS

10.1. Posting of Information on Publicly Available Clinical Trial Registers

Study information from this protocol will be posted on publicly available clinical trial registers before enrollment of subjects begins.

10.2. Regulatory and Ethical Considerations, Including the Informed Consent Process

Prior to initiation of a site, GSK will obtain favourable opinion/approval from the appropriate regulatory agency to conduct the study in accordance with ICH Good Clinical Practice (GCP) and applicable country-specific regulatory requirements.

The study will be conducted in accordance with all applicable regulatory requirements, and with GSK policy.

The study will also be conducted in accordance with ICH GCP, all applicable subject privacy requirements, and the guiding principles of the current version of the Declaration of Helsinki. This includes, but is not limited to, the following:

- IRB/IEC review and favorable opinion/approval of the study protocol and amendments as applicable
- Signed informed consent to be obtained for each subject before participation in the study (and for amendments as applicable)
- Investigator reporting requirements (e.g. reporting of AEs/SAEs/protocol deviations to IRB/IEC)
- GSK will provide full details of the above procedures, either verbally, in writing, or both.

10.3. Quality Control (Study Monitoring)

In accordance with applicable regulations including GCP, and GSK procedures, GSK or delegated monitors will contact the site prior to the start of the study to review with the site staff the protocol, study requirements, and their responsibilities to satisfy regulatory, ethical, and GSK requirements.

When reviewing data collection procedures, the discussion will also include identification, agreement and documentation of data items for which the CRF will serve as the source document.

GSK will monitor the study and site activity to verify that the:

- Data are authentic, accurate, and complete.
- Safety and rights of subjects are being protected.
- Study is conducted in accordance with the currently approved protocol and any other study agreements, GCP, and all applicable regulatory requirements.

The investigator and the head of the medical institution (where applicable) agrees to allow the monitor direct access to all relevant documents

10.4. Quality Assurance

To ensure compliance with GCP and all applicable regulatory requirements, GSK may conduct a quality assurance assessment and/or audit of the site records, and the regulatory agencies may conduct a regulatory inspection at any time during or after completion of the study.

In the event of an assessment, audit or inspection, the investigator (and institution) must agree to grant the advisor(s), auditor(s) and inspector(s) direct access to all relevant

documents and to allocate their time and the time of their staff to discuss the conduct of the study, any findings/relevant issues and to implement any corrective and/or preventative actions to address any findings/issues identified.

